6.2 Study Specified Dose Modifications for Hematologic Toxicities

| Neutropenia | Management/Next Dose for Hydroxychloroquine |
|---|--|
| ≤ Grade 1 | No change in dose |
| Grade 2 | Hold until ≤ Grade 1. Resume at same dose level. |
| Grade 3 or 4 | Hold* until < Grade 2. Resume at one dose level lower, if indicated.** |
| Grade 4 | Off protocol therapy |
| *Patients requiring a delay of >2 weeks should go off protocol therapy. **Patients requiring > two dose reductions should go off protocol therapy. | |

| Thrombocytopenia | Management/Next Dose for Hydroxychloroquine |
|---|--|
| ≤ Grade 1 | No change in dose |
| Grade 2 | Hold until ≤ Grade 1. Resume at same dose level. |
| Grade 3 or 4 | Hold* until < Grade 2. Resume at one dose level lower, if indicated.** |
| *Patients requiring a delay of >2 weeks should go off protocol therapy. **Patients requiring > two dose reductions should go off protocol therapy. | |

All other grade 3 or 4 toxicities should be discussed with the PI.

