5.4 Definition of Dose-Limiting Toxicity

Subjects will be evaluated for toxicity according to the Common Terminology Criteria for Adverse Events (CTCAE) of the National Cancer Institute (NCI) version 4.0 available at: www.ctep.gov. A DLT is defined as any of the below treatment emergent toxicities with attribution (possibly, probably or definitely related) to the study medication that occurs during or within 30 days of the last dose of hydroxychloroquine.

Non-Hematologic:

- \geq Grade 3 or 4 neuropathy
- \geq Any Grade 3 or 4 adverse event (excluding grade 3 nausea, vomiting, diarrhea lasting < 7 days or grade 3 fatigue). Note: Abnormal non-hematologic laboratory values $>$ grade 3 will be considered a DLT if they are determined to be clinically significant and possibly, probably or definitely related to study drug. If baseline value is elevated (or decreased) prior to enrollment, an increase (or decrease) will not be considered a DLT unless it worsens by 2 grades and is determined to be clinically significant by the treating investigator.
- \geq Grade 3 nausea, vomiting, or diarrhea lasting > 7 days despite maximal antiemetic/antidiarrheal therapy
- Grade 5 toxicity

Hematologic:

- Grade 4 neutropenia ($ANC < 0.5 \times 10^9/L$) lasting for ≥ 7 days
- Febrile neutropenia ($ANC < 1.0 \times 10^9/L$ with a fever $\geq 38.3^\circ C$)
- Grade 4 thrombocytopenia (platelets $< 25.0 \times 10^9/L$) lasting ≥ 7 days despite dose delay
- Grade 3-4 thrombocytopenia associated with bleeding
- Grade 5 toxicity

Management and dose modifications associated with the above adverse events are outlined in Section 6.

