5.6 Duration of Therapy

In the absence of treatment delays due to adverse event(s), treatment will continue for 14 days or until one of the following criteria applies:

- Disease progression,
- Intercurrent illness that prevents further administration of treatment,
- Unacceptable adverse event(s),
- Patient decides to withdraw from the study, or
- General or specific changes in the patient's condition render the patient unacceptable for further treatment in the judgment of the investigator.

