8.7 Precautions: General

Antimalarial compounds should be used with caution in patients with hepatic disease or alcoholism or in conjunction with known hepatotoxic drugs. Periodic blood cell counts should be made if patients are given prolonged therapy. If any severe blood disorder appears which is not attributable to the disease under treatment, discontinuation of the drug should be considered. The drug should be administered with caution in patients having G-6-PD (glucose-6-phosphate dehydrogenase) deficiency.

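### The neutropenia table in Section 6.2 gives Grade 4 two incompatible instructions: restart at a lower dose if indicated, or stop for good

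*Combined protocol and SAP*

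**What the plan says.** Section 6.2 sets out what to do with hydroxychloroquine when neutropenia occurs. After rows for Grade 1 or lower and for Grade 2, the table has these two consecutive rows:

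- "Grade 3 or 4 | Hold* until < Grade 2. Resume at one dose level lower, if indicated"
- "Grade 4 | Off protocol therapy"

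Footnotes to the first of these take a patient off therapy if the delay exceeds two weeks or if more than two dose reductions are needed. Below the tables, Section 6.2 adds: "All other grade 3 or 4 toxicities should be discussed with the PI".

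Section 5.4 lists "Grade 4 neutropenia" lasting at least 7 days, and "Febrile neutropenia", among the hematologic dose-limiting toxicities (DLTs). It then says: "Management and dose modifications associated with the above adverse events are outlined in Section 6".

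**The concern.** A dose-modification table should give one action for each grade. Here a patient with Grade 4 neutropenia falls under two rows. A clinician who restarts the drug after recovery follows one row and breaches the other, so identical patients could be managed differently by staff who each cite the table.

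The decision at stake is re-exposure to study drug after a neutrophil count below 0.5 × 10⁹/L, in patients who under Section 3.2 must be candidates for curative-intent surgery. Section 7.3 lists bone marrow depression and agranulocytosis as reactions to hydroxychloroquine with unknown frequency, so the event is foreseeable even if rare.

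**Working it through.** The main check compares texts. The only arithmetic concerns how much dosing time a restart could use.

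**1. Which rows cover Grade 4.** The neutropenia table has four grade rows: Grade 1 or lower, Grade 2, Grade 3 or 4, and Grade 4. Two of the four cover Grade 4. One leads to a hold and a possible lower-dose restart, the other to permanent discontinuation.

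**2. How the other tables compare.** There are six toxicity tables: nausea/vomiting, diarrhea, visual changes and dermatitis in Section 6.1 (4), and neutropenia and thrombocytopenia in Section 6.2 (2); 4 + 2 = 6. All six have the combined Grade 3 or 4 row. Only neutropenia has a separate Grade 4 row. This suggests that the stop rule was added without trimming the row above it, but the documents do not prove it.

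**3. Whether any other text decides between the rows.**

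- *Footnotes:* they limit the length of the delay and the number of reductions. Neither confines the combined row to Grade 3.
- *Closing line of Section 6.2:* it covers toxicities other than those tabulated, so it does not reach neutropenia.
- *Section 5.4:* it returns the reader to Section 6, where the conflict sits.
- *Section 5.6:* it ends treatment for unacceptable adverse events and allows the investigator to stop on judgement. It does not say whether Grade 4 neutropenia is unacceptable.
- *Section 8.7:* "If any severe blood disorder appears which is not attributable to the disease under treatment, discontinuation of the drug should be considered". This leans towards stopping but does not require it.

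None of these settles the matter.

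**4. Whether the DLT definition closes the gap.** Under the hematologic criteria in Section 5.4, Grade 4 neutropenia is a DLT only if it lasts at least 7 days or meets the febrile criterion. A short afebrile episode is not a DLT, yet it is the kind most likely to recover in time for a restart. Even an episode that is a DLT is referred back to Section 6 for management.

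**5. Whether there is time to restart.** Inputs: planned dosing runs to day 14 (Section 5.2); a 7-day extension takes it to day 21 (Section 5.2, Study Calendar); on-treatment blood counts are scheduled at days 7 and 14 (Study Calendar).

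Dosing days left = last dosing day − day of the blood count.

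- Day 7 count, planned course: 14 − 7 = 7 days (days 8 to 14).
- Day 7 count, with extension: 21 − 7 = 14 days (days 8 to 21).
- Day 14 count, planned course: 14 − 14 = 0 days.
- Day 14 count, with extension: 21 − 14 = 7 days (days 15 to 21).

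These are upper limits, because the hold itself uses some of the days. Within the planned course, a Grade 4 count found on day 7 and still present 7 days later (7 + 7 = day 14) leaves no dosing day. Counted from the day 7 sample, a restart in the planned course therefore follows only an episode shorter than 7 days, which is not a DLT unless febrile.

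**6. What cannot be computed.** The protocol gives no rate of Grade 4 neutropenia on hydroxychloroquine, so no expected number of affected patients follows.

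**The case against.** The strongest reply is that the conflict would rarely matter. Nothing compels a restart: the combined row requires recovery to below Grade 2, a lower dose and a judgement that resuming is indicated, and Section 5.6 lets the investigator stop at any time. Stopping satisfies both rows. Many staff would also let the separate, unconditional Grade 4 row override the general one. All this is fair and limits the harm. It does not remove the conflict: the protocol states no such precedence, and that reading makes the mention of Grade 4 in the combined row an error, which is the point raised here.

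Other objections partly stand:

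- **Day counts.** Sections 5.2 and the Study Calendar allow the extension for unforeseen delays and do not say whether a toxicity hold qualifies, so the 14-day figure and the 7-day figure after day 14 depend on that. The statement that a restart in the planned course follows only a non-DLT episode depends on counting from the day 7 sample. No earlier on-treatment count is scheduled, so true onset could be earlier and the episode longer.
- **Choice of fix.** Deleting the Grade 4 row, to match the thrombocytopenia table, would also remove the conflict, and the documents do not show which was intended. Section 8.7 asks only that stopping be considered, so it supports the stricter choice without dictating it.

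**Conclusion.** The concern holds. The Section 6.2 neutropenia table authorises, after Grade 4 neutropenia, a restart that its next row forbids, and nothing else in the protocol resolves it. One of six toxicity tables is affected, and two of its four grade rows conflict.

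This rests on the wording alone and on no assumed rate. The practical effect is probably small: a course of 14 days, 18 patients, and an event of unknown but likely low frequency. The DLT definition, the sample size and the simulation results in Table 1 are unaffected. It is still an operative safety instruction that should be corrected.

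**What to change.** In the Section 6.2 neutropenia table, change the label of the combined row from Grade 3 or 4 to Grade 3, and leave the Grade 4 row as it stands. This keeps the explicit stop rule, is the more protective of the two possible corrections, and fits the precaution in Section 8.7. If the sponsor did intend a restart to be possible after Grade 4, the alternative is to delete the Grade 4 row; one of the two must go.

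The cost is one row label, with no extra patients, visits or procedures. Section 4.1 requires committee, sponsor and ethics board approval for amendments that are not administrative. A change to a dose-modification rule may fall under that, so it is sensible to include it in the next amendment.

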7. ADVERSE EVENTS: LIST AND REPORTING REQUIREMENTS

Adverse event (AE) monitoring and reporting is a routine part of every clinical trial. The following list of AEs (Section 7.1) and the characteristics of an observed AE (Section 7.2) will determine whether the event requires expedited reporting (via Medwatch Forms) **in addition** to routine reporting.

7.1 Expected Toxicities for Hydroxychloroquine

7.2 Precautions

Dermatologic reactions to hydroxychloroquine sulfate tablets may occur and, therefore, proper care should be exercised when they were administered to any patient receiving a drug with a significant tendency to produce dermatitis.

The methods recommended for early diagnosis of "chloroquine retinopathy" consist of (1) fundoscopic examination of the macula for fine pigmentary disturbances or loss of the foveal reflex and (2) examination of the central visual field with a small red test object for pericentral or paracentral scotoma or determination of retinal thresholds to red. Any unexplained visual symptoms, such as light flashes or streaks should also be regarded with suspicion as possible manifestations of retinopathy.

If serious toxic symptoms occur from overdosage or sensitivity, it has been suggested that ammonium chloride (8 g daily in divided doses for adults) be administered orally three or four days a week for several months after therapy has been stopped, as acidification of the urine increases renal excretion of the 4-aminoquinoline compounds by 20 to 90 percent. However, caution must be exercised in patients with impaired renal function and/or metabolic acidosis.

7.3 Adverse Reactions

The following Council for International Organizations of Medical Sciences (CIOMS) frequency rating is used, when applicable: Very common $\geq 10\%$; Common ≥ 1 and $<10\%$; Uncommon ≥ 0.1 and $<1\%$; Rare ≥ 0.01 and $<0.1\%$; Very rare $<0.01\%$; Not known (frequency cannot be estimated from available data).

Blood and lymphatic system disorders

Not known: Bone marrow depression, anemia, aplastic anemia, agranulocytosis, leucopenia, thrombocytopenia.

Cardiac disorders

Not known: Cardiomyopathy, which may result in cardiac failure and in some cases a fatal outcome.

Chronic toxicity should be considered when conduction disorders (bundle branch block/atrioventricular heart block) as well as biventricular hypertrophy are found. Drug discontinuation may lead to recovery.

Ear and labyrinth disorders

Uncommon: Vertigo, tinnitus

Not known: Hearing loss including cases of irreversible hearing loss.

Eye disorders

Common: Blurring of vision due to a disturbance of accommodation which is dose dependent and reversible.

Uncommon: Maculopathies which may be irreversible.

Retinopathy with changes in pigmentation and visual field defects. In its early form it appears reversible upon discontinuation of the drug. If allowed to develop however, there may be a risk of progression even after treatment withdrawal.

Patients with retinal changes may be asymptomatic initially, or may have scotomatous vision with paracentral, pericentral ring types, temporal scotomas, abnormal color visions, reduction in visual acuity, night blindness, difficulty reading and skipping words. Corneal changes including edema and opacities. They are either symptomless or may cause disturbances such as halos around lights especially at night, blurring of vision or photophobia. They may be transient or are reversible upon discontinuation of therapy.

Not known: Macular degeneration which may be irreversible.

Gastrointestinal disorders

Very common: Abdominal pain, nausea

Common: Diarrhea, vomiting

These symptoms usually resolve immediately upon reducing the dose or upon stopping the treatment.

Hepatobiliary disorders

Uncommon: Abnormal liver function tests

Not known: Fulminant hepatic failure

Immune system disorders

Not known: Urticaria, angioedema, bronchospasm.

Metabolism and nutrition disorders

Common: Anorexia (usually resolves immediately upon reducing the dose or upon stopping the treatment).

Not known: hypoglycemia

HYDROXYCHLOROQUINE may exacerbate porphyria.

Musculoskeletal and connective tissue disorders

Uncommon: Sensory motor disorders

Not known: Skeletal muscle palsies or skeletal muscle myopathy or neuromyopathy leading to progressive weakness and atrophy of proximal muscle groups. Depression of tendon reflexes, abnormal results of nerve conduction tests. Myopathy may be reversible after drug discontinuation, but recovery may take many months.

Nervous system disorders

Common: Headache

Uncommon: Dizziness

Not known: Convulsions

Psychiatric disorders

Common: Affect lability

Uncommon: Nervousness

Not known: Psychosis, suicidal behaviour

Skin and subcutaneous tissue disorders

Common: Skin rash, pruritus

Uncommon: Pigmentary changes in skin and mucous membranes, bleaching of hair, alopecia. These usually resolve readily upon cessation of therapy.

Not known: Bullous eruptions (including urticarial, morbilliform, lichenoid, maculopapular, purpuric, erythema annulare centrifugum), toxic epidermal necrolysis, erythema multiforme, Stevens-Johnson syndrome, Drug Rash with Eosinophilia and Systemic Symptoms (DRESS syndrome), photosensitivity, exfoliative dermatitis, acute generalized exanthematous pustulosis (AGEP).

AGEP has to be distinguished from psoriasis, although HYDROXYCHLOROQUINE may precipitate attacks of psoriasis. It may be associated with fever and hyperleukocytosis. Outcome is usually favorable after discontinuation of drug.

For a comprehensive list of adverse events please refer to the package insert.

7.4 Adverse Event Characteristics

- **CTCAE term (AE description) and grade:** The descriptions and grading scales found in the revised NCI Common Terminology Criteria for Adverse Events (CTCAE) version 4.0 will be utilized for AE reporting. All appropriate treatment areas should have access to a copy of the CTCAE version 4.0. A copy of the CTCAE version 4.0 can be downloaded from the CTEP web site http://ctep.cancer.gov/protocolDevelopment/electronic_applications/ctc.htm.
- **For expedited reporting purposes only:**
 - AEs for the agent(s) that are listed above should be reported only if the adverse event varies in nature, intensity or frequency from the expected toxicity information which is provided.
 - Other AEs for the protocol that do not require expedited reporting are outlined in the next section (Expedited Adverse Event Reporting) under the sub-heading of Protocol-Specific Expedited Adverse Event Reporting Exclusions.
- **Attribution of the AE:**
 - Definite – The AE *is clearly related* to the study treatment.
 - Probable – The AE *is likely related* to the study treatment.
 - Possible – The AE *may be related* to the study treatment.
 - Unlikely – The AE *is doubtfully related* to the study treatment.
 - Unrelated – The AE *is clearly NOT related* to the study treatment.

7.5 Expedited Adverse Event Reporting

7.5.1 For MCC Investigator-Initiated Trials (IITs), investigators **must** report to the Overall PI any serious adverse event (SAE) that occurs after the initial dose of study treatment, during treatment, or within 30 days of the last dose of treatment on the local institutional SAE form. This applies to the following categories:

- **Grade 3 (severe) Medical Events** – Only events that are Unexpected and Possibly, Probably or Definitely Related / Associated with the Intervention.
- **ALL Grade 4 (life threatening or disabling) Medical Events** – Unless expected AND specifically listed in protocol as not requiring reporting.
- **ALL Grade 5 (fatal) Events** regardless of study phase or attribution

Note: If subject is in Long Term Follow Up, death is reported at continuing review.

Note: Abnormal laboratory values are not considered medical events, unless determined to be causative of SAE by the investigator or grade 5.

7.5.2 The following table outlines the required forms and reporting structure for clinical trials.

| Study type | Expedited reporting to MCC | Expedited reporting to External Agency | Non-expedited AE | Form | IRB |
|---|--|--|--------------------------------|---|---|
| IIT where MCC investigator holds the IDE or IND | 
 • Grade 3 – Unexpected AE PLUS Possibly, Probably or Definitely Related • ALL Grade 4 Unless expected AND listed in protocol as not requiring reporting. • ALL Grade 5 (fatal) Events | FDA: Suspected AE that is serious and Unanticipated (not listed in IDB or consent) | OnCore and DSMC reporting only | 
Mandatory Medwatch 3500a for Serious and unanticipated
 
OnCore for all AEs, including SAEs
 | Yes if it meets the IRB reporting requirements: Unanticipated Problem and/or Serious AE (use IRB AE reporting form for all correspondence with IRB) |
| IIT by MCC investigator of commercially available agent (non-IND and non-IDE) | 
 • Grade 3 – Unexpected AE PLUS Possibly, Probably or Definitely Related • ALL Grade 4 Unless expected AND listed in protocol as not requiring reporting. | FDA: Suspected AE that is serious and Unanticipated (not listed in IDB or consent) | OnCore and DSMC reporting only | 
Voluntary Medwatch 3500 for Serious and unanticipated
 
OnCore for all AEs, including SAEs
 | |

| | | | | | |
|--|--|--|--|--|--|
| | 
 ALL Grade 5 (fatal) Events | | | | |
|--|--|--|--|--|--|

7.5.3 MCC Expedited Reporting Guidelines for MCC IITs

Investigators within MCC will report SAEs directly to the MCC DSMC per the MCC DSMC SOP and the University of Kentucky IRB reporting policy.

| Attribution | MCC Reportable AEs | | | | |
|--|-----------------------|-------------------------|------------------------------|---------------------|---------------------------------|
| | Gr. 2 & 3 AE Expected | Gr. 2 & 3 AE Unexpected | Gr. 4 AE Expected | Gr. 4 AE Unexpected | Gr. 5 AE Expected or Unexpected |
| Unrelated Unlikely | Not required | Not required | 5 calendar days [#] | 5 calendar days | 24 hours* |
| Possible Probable Definite | Not required | 5 calendar days | 5 calendar days [#] | 5 calendar days | 24 hours* |
| # If listed in protocol as expected and not requiring expedited reporting, event does not need to be reported. | | | | | |
| * For participants enrolled and actively participating in the study or for AEs occurring within 30 days of the last intervention, the AE should be reported within 24 business hours of learning of the event. | | | | | |

Other investigative sites will report SAEs to their respective IRB according to the local IRB's policies and procedures in reporting adverse events. A copy of the submitted institutional SAE form should be forwarded to the Overall PI within the timeframes detailed in the table above.

The Overall PI will submit SAE reports from outside institutions to the MCC DSMC and UK IRB according to IRB policies and procedures in reporting adverse events:
http://www.research.uky.edu/ori/SOPs_Policies/C2-0350-Unanticipated_Problems_Adverse_Events_SOP.pdf.

7.6 Expedited Reporting to External Agencies

The Overall PI will comply with the policies of all external funding agencies and the UK IRB regarding expedited reporting, as per the UK IRB's SOP:
http://www.research.uky.edu/ori/SOPs_Policies/C4-0150-Mandated_Reporting_to_External_Agencies_SOP.pdf.

7.6.1 Expedited Reporting to the Food and Drug Administration (FDA)

Include this section and text for investigator-held IDE and IND studies, including gene transfer. If this is not an investigator-held IDE or IND study, this section and text should be deleted.

The Overall PI, as study sponsor, will be responsible for all communications with the FDA. The Overall PI will report to the FDA, regardless of the site of occurrence, any serious adverse event that meets the FDA's criteria for expedited reporting following the reporting requirements and timelines set by the FDA.

7.6.2 Expedited Reporting to Hospital Risk Management

Participating investigators will report to the UK Office of Risk Management any participant safety reports or sentinel events that require reporting according to institutional policy.

7.7 Routine Adverse Event Reporting

All Adverse Events **must** be reported in routine study data submissions to the Overall PI on the OnCore case report forms. **AEs reported through expedited processes (e.g., reported to the IRB, FDA, etc.) must also be reported in routine study data submissions.**

[figure not shown]
8. PHARMACEUTICAL INFORMATION

A list of the adverse events and potential risks associated with the investigational or commercial agents administered in this study can be found in Section 7.1.

8.1 Commercial Agent: Hydroxychloroquine.

8.2 Description

Hydroxychloroquine sulfate, USP is a colorless crystalline solid, soluble in water to at least 20 percent; chemically the drug is 2-[[4-[(7-Chloro-4-quinoly) amino]pentyl] ethylamino] ethanol sulfate (1:1). Hydroxychloroquine sulfate, USP has the following structural formula:

Molecular Formula: C₁₈H₂₆ClN₃O₄.H₂SO₄

Molecular Weight of 433.95

Each tablet, for oral administration, contains 200 mg hydroxychloroquine sulfate, USP (equivalent to 155 mg base). In addition, each tablet contains the following Inactive Ingredients: colloidal silicon dioxide, dibasic calcium phosphate, hypromellose, macrogol/PEG 3350, magnesium stearate, polysorbate 80, pregelatinized starch, talc, and titanium dioxide.

Hydroxychloroquine sulfate tablets, USP are white, to off-white, capsule-shaped tablets, debossed with "HCQS" on one side and plain on the reverse side and are available in bottles of 10, 100, 500 and 1000.

| | |
|------------------|-----------------|
| NDC 63304-296-03 | Bottles of 10 |
| NDC 63304-296-01 | Bottles of 100 |
| NDC 63304-296-05 | Bottles of 500 |
| NDC 63304-296-10 | Bottles of 1000 |

